6.1 Adverse event definitions

The term "adverse event" could include any of the following events which develop or increase in severity during the course of the study, after administration of the study product:

a) Any unfavorable and unintended signs, symptoms or disease temporally associated with the use of a medicinal product, whether or not considered related to the condition under study and the study product;

b) Any abnormality detected during physical examination.

The medical conditions present at the initial trial visit that do not worsen in severity or frequency during the trial will not be defined as AEs but be considered baseline medical conditions. For the purpose of this trial, disease progression and relapse will be considered as treatment failure, not as an AE.

The observation time for AEs starts when the treatment is initiated until day 21 (3 weeks after last drug administration).

These data will be recorded on the appropriate case report form (CRF) sections, regardless of whether they are thought to be associated with the study or the drug under investigation. Associated with the use of the drug means that there is a reasonable possibility that the event may have been caused by the drug (see also relatedness definitions below).

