7.4 Description of data management and data quality control

The investigators are responsible for an adequate data quality. Prior to the initiation of the study, a short investigator's meeting will be held with the investigators and their study coordinators and a member from Swiss

Page 156 of 176

TPH. This meeting will include a detailed discussion of the protocol, performance of study procedures (standard operating procedures (SOPs) from previous studies available on site), CRF completion, and specimen collection and diagnostic methods.

The data produced from this research project will fall into the following categories:

- Eggs counts of *T. trichiura*, *A. lumbricoides* and hookworm and infection status with *S. stercoralis* based on participants' stool samples analyzed using the Kato-Katz and Baermann technique, respectively, before (baseline) and at 3 time points after treatment (follow-ups after 3 weeks, 6 and 12 months). Presence of fecal occult blood and elevated calprotectin levels will be evaluated and recorded applying RDTs on the same stool samples and assessment time points.
- 2. Personal information such as name, age, gender and household composition of trial participants.
- 3. Anthropometric and clinical characteristics of the trial participants collected using the study's CRF such as weight, height, skinfold thickness, blood pressure, temperature, hemoglobin level, infection status with *Plasmodium spp.*, any abnormal medical condition or chronic disease as well as pregnancy in female participants 10 years and above.
- 4. Number and type of AEs registered in the CRF actively probed for 3 and 24 hours after treatment. The same data will be collected during the collection of the first sample at the 3-week follow-up.
- 5. Scales for participant-rated treatment satisfaction and self-rated physical functioning in school-aged children captured on different time points (i.e. 3 weeks and 6 months and baseline, 6 and 12 months after treatment, respectively) and recorded on the CRF.
- 6. Concentration levels of blood and biochemical parameters together with indicators for micronutrient status as well as presence of *S.stercoralis* antibodies in urine before (baseline) and at 3 time points after treatment (follow-ups after 3 weeks, 6 and 12 months).
- 7. Household-level data on socioeconomic characteristics, presence and use of water and sanitation as well as hygiene-related attitudes and practices.

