- 33. ICH Expert Working Group: ICH harmonised tripartite guideline. Clinical safety data management: definitions and standards for expedited reporting E2A. International conference on harmonisation of technical requirements for registration of pharmaceuticals for human use; 1994.
- 34. Duggan MB: Anthropometry as a tool for measuring malnutrition: impact of the new WHO growth standards and reference. *Ann Trop Paediatr* 2010, **30**(1):1-17.
- 35. Wang Y, Chen H: Use of Percentiles and Z-Scores in Anthropometry. In: *Handbook of Anthropometry*. Edited by Preedy V. New York: Springer; 2012: 29-48.

Page 163 of 176

7. Statistical Analysis Plan (SAP)

Clinical trial protocol title:	Efficacy and safety of ivermectin and albendazole co-administration in school-aged children and adults infected with Trichuris trichiura : a multi-country randomized controlled trial
Principal Investigator	[name]
ClinicalTrials.gov identifier	03527732
Author	[name]
Version/Date	v1.0/14.9.2020

Page 164 of 176

Contents

Signatures	
Introduction	
Study Objectives and Endpoints	
Study Objectives	
Primary Objective	167
Secondary Objectives	
Study Endpoints	
Primary	
Secondary	
Statistical Hypotheses	
Study Design	
Planned Analyses	169
Interim Analyses	
Final Analysis	
Sample size consideration	
Populations for analysis	
Subgroup analyses	
Data handling conventions and missing data	
Protocol deviations	170
Demographics and other baseline characteristics	171
Efficacy analysis	171
Safety analysis	

Page 165 of 176

Signatures

The following persons have read and agreed on the SAP:

[name]

Trial Statistician

Date of signature 14.9.2020

[name]

Principal investigator

Date of signature 14.9.2020

[name]

Introduction

This Statistical Analysis Plan (SAP) is based on the current trial protocols versions v1.01_19.09.2018 (Lao PDR), v1.03_22.11.2018 (Côte d'Ivoire) and v1.01_13.2.18_(Zanzibar).

Where statistical methods differ substantially between this SAP and the protocol, the differences will be identified in the SAP.

This SAP describes the datasets and the statistical methods to be used for the reporting and analysis of all data collected 3 weeks after treatment in **three randomized controlled trials**. If a future protocol amendment necessitates a substantial change to the statistical analysis of the trial data, this SAP will be amended accordingly.

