This is a multi-center, blinded, randomised, SoC-controlled, parallel-group, single-dose, superiority trial. Participants in the albendazole monotherapy arm will receive a matching ivermectin placebo. Double blinded (study participants, trial team/researchers conducting the treatment and outcome assessors) using repacked tablets including appearance-matched placebos. Computer-generated stratified block randomization code. The random allocation sequence with varying random blocks of four or eight and stratified by 2 levels of baseline infection intensity. Tablets together with the respective treatment arm label were pre-packed by researchers not involved in this trial into small opaque envelopes labelled with the unique IDs to ensure allocation concealment.

Time and Events Table

	Screening	Baseli	ne/Tr	eatment/	Safety	Follow up						
	-21 to -1		Η	lours		Days						
	days	0		3	24	21	180 ^a	185ª	360ª			
Diagnosis (stool and urine examination)	Х					Х	Х		Х			
Gut morbidity (stool RDTs)	Х					Х	Х		Х			
Informed consent	Х		ent									
Demographics	Х		eatmo									
Medical history		Х	nd tr					ment				
Clinical examination		Х	ion a				Х	treat	Х			
Pregnancy testing		Х	mizat				Х	ve re-				
Hemoglobin measurement		Х	opue				Х	electiv	Х			
Plasmodium co-infection		Х	ß				Х	Š	Х			
Venous blood examination		Х				Х	Х		Х			
Physical functioning		Х					Х		Х			
Capturing AEs				Х	Х	Х						
Capturing SAE				Х	Х	Х						
Treatment satisfaction				Х		Х	Х					

^a not subject of this SAP

Page 169 of 176

Planned Analyses

Interim Analyses

Because of the short follow-up period, no interim analyses are planned.

Final Analysis

The database will be locked after all subjects have completed the study and the data have been entered, validated and all queries are resolved.

Sample size consideration

Each of the three trials was powered to detect a difference with 90% power at a two-sided 5% significance level assuming a CR of albendazole against *T. trichiura* is 30% and 50% in the albendazole-ivermectin treatment regimen. We anticipate to enrol 143 participants per study arm (including a potential loss to follow-up of 15%). For sub group analysis the data from all trials will be pooled to ensure sufficient power. Further details on the justification of study subjects are provided in the trial protocols.

Populations for analysis

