	treatment					
	After treatment					
Cure rat	e, %					
N partic	ipants cured (%)					
	From light infection					
	From moderate infection					
	From heavy infection					
Geometric mean EPG						
	Before treatment					
	After treatment					
Egg-red	uction rate, %					
S. sterce	oralis ^a					
No. of p infection	participants positive	for				
	Before treatment					
	After treatment					
Cure rat	e, %					

EPG: eggs per gram of stool

^a S. stercoralis infection was assessed qualitatively only (positive vs negative) in stool samples collected in Lao PDR

Page 175 of 176

Safety analysis

Adverse events will be analysed descriptively and summarized (for each country) as outlined in the 2 tables below.

Table: Adverse events assessed at baseline, 3 hours and 24 hours post treatment by treatment arm

	Before treatment	3h post treatment	24h post treatment	After 24h
ALB				
Total participants assessed				
Participants with AE				
% participants with AE				
Number of AEs				
IVM-ALB				
Total participants assessed				
Participants with AE				
% participants with AE				
Number of AEs				
TOTAL				
Total participants assessed				
Participants with AE				
% participants with AE				
Number of AEs				

Page 176 of 176

	Baseline					3h post-treatment					24h post-treatment							
	AL	B	IVN	1-	ΤΟ	ГА	AL	B	IVN	1-	TO	FAL	AL	B	IVN	1-	тот	AL
			ALI	B	L				ALI	3					ALI	B		
Adver	N	N	N	N	N	N	N	N	N	Ν	N	N	N	N	N	N	N	N
se	A	Gr	A	Gr	A	Gr	A	Gr	A	Gr	An	Gr	A	Gr	A	Gr	An	Gr
event	nv	ad	nv	ad	nv	ad	nv	ad	nv	ad	v	ad	nv	ad	nv	ad	v	ad
event	gr	e	gr	e	gr	e	gr	e	gr	e	gr	e	gr	e	gr	e	gra	e
	ad	>2	ad	>2	ad	>2	ad	>2	ad	>2	ad	>2	ad	>2	ad	>2	de	>2
	e		e		e		e		e		e		e		e		au	
							-		-		-		-		-			
Heada																		
che																		
Abdo																		
minal																		
pain																		
Itching																		
Nause																		
а																		
Vomiti																		
ng																		
Diarrh																		
ea																		
Fever																		
Allergi																		
C																		
reactio																		
n																		
11																		
Other																		

Table: Specific adverse events by treatment arm and time point

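### The SAP gives no breakdown of adverse events by type or grade after 24 hours and no summary of SAEs by arm, although both are captured to day 21

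*Combined protocol and SAP*

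**What the plan says.** The SAP's Introduction sets its scope as the "reporting and analysis of all data collected 3 weeks after treatment". Its Time and Events Table has one row for AEs and another labelled "Capturing SAE". Both are marked at 3 hours, 24 hours and day 21, and only days 180, 185 and 360 are footnoted as outside the SAP. Safety is named in the SAP's primary objective, is its first secondary objective, and appears again among its secondary endpoints.

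The SAP's Safety analysis section then fixes the output: "Adverse events will be analysed descriptively and summarized (for each country) as outlined in the 2 tables below". The first is headed "Table: Adverse events assessed at baseline, 3 hours and 24 hours post treatment by treatment arm". The second is headed "Table: Specific adverse events by treatment arm and time point".

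On collection, section 6.1 of each country protocol says: "The observation time for AEs starts when the treatment is initiated until day 21 (3 weeks after last drug administration". Section 6.2 of each schedules AE interviews at 3 hours, 24 hours and 3 weeks, and has the start, length, intensity, seriousness and causality of every AE entered on the CRF. Section 7.4 of the Laos and Côte d'Ivoire protocols, after listing number and type of AEs at 3 and 24 hours, adds: "The same data will be collected during the collection of the first sample at the 3-week follow-up".

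**The concern.** The plan collects the nature, intensity and seriousness of events to day 21 but does not carry that information into its results. Followed as written, a severe allergic reaction or a hospital admission on day 5 would enter the SAP tables as one participant and one event in the *After 24h* column, with nothing to show what it was, how bad it was or that it was serious.

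At stake is a stated objective. A reader of the planned tables could compare the arms on kind and severity of event for the first day only, and could not compare them on SAEs at any time. The protocols set up no data and safety monitoring board (section 10.4 in each), so no other planned step compares safety by arm.

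**Working it through.** The plan gives no figure to reproduce. The check sets what is captured against what is tabulated.

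| Item | Captured | Planned in the SAP tables |
|---|---|---|
| Overall AE counts, 3 h and 24 h | Yes | Yes, first table |
| Overall AE counts after 24 h | Yes (3-week interview) | Yes, first table, *After 24h* column |
| AE type and grade, 3 h and 24 h | Yes | Yes, second table |
| AE type and grade after 24 h | Yes | No |
| SAEs, any time | Yes (3 h, 24 h, day 21) | No row, column or listing |

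**First table.** Its columns are before treatment, 3 h, 24 h and after 24 h. For each arm and the total, its rows are participants assessed, participants with an AE, the percentage, and the number of AEs. No row gives type, grade or seriousness. The title names only baseline, 3 h and 24 h, so it does not describe its own last column.

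**Second table.** Three time blocks (baseline, 3 h, 24 h) × three groups (ALB, IVM-ALB, total) × two columns (any grade, grade above 2) = 18 columns. All 18 can be read in the document, so a later block has not been lost in text extraction.

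**Interviews.** There are three after treatment: 3 h, 24 h and 3 weeks. The third has no breakdown by type or grade: 1 of 3 (33%).

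**Could another section supply what is missing?** Section 7.3 of each protocol plans only a descriptive difference in the proportion reporting AEs before and after treatment. The grade-above-2 column cannot stand in for SAEs: section 6.1.4 of each protocol says that a severe event need not be a serious one, and the column ends at 24 h anyway.

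**SAE window by country.** Section 6.1.4 runs SAE reporting from consent to day 21 in Laos and Côte d'Ivoire. In Pemba it ends 24 hours after treatment. The Pemba schedule of visits (section 4.6) and the SAP's Time and Events Table both mark SAE capture at day 21. Pemba's passages therefore contradict each other, and an SAE summary by country has no agreed window there.

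**Support for the 3-week data in each country.** Laos and Côte d'Ivoire state in section 7.4 that number and type are collected again at 3 weeks. Pemba's section 7.4 has no such list. For Pemba the point rests on section 6.2, which schedules the 3-week interview and requires the same details for every AE.

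**The case against.** The strongest reply is that nothing is lost from the record. Every AE is documented on the CRF. Every SAE is notified to the sponsor-investigator within 24 hours, followed by a written narrative and SAE form within a further 48 hours (section 6.3), and goes on to ethics committees and health authorities (section 6.4). This is correct, and it rules out the inference that SAEs go unrecorded or unreported. But it is case-by-case notification, not a planned result by arm.

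Second, a reader might infer that everything after the first day is missing from the results. The *After 24h* column shows otherwise: counts and percentages by arm are planned. What is missing is the breakdown.

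Third, a reader might note that 20 of the 21 observation days lie after 24 hours and conclude that 95% of the safety information is dropped. Days are not events. The documents give no AE rate after 24 hours, and one interview covers those days.

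Fourth, the SAP plans only a descriptive safety summary, and its sole hypothesis concerns efficacy. It would be wrong to say that the tables fail to support a planned claim of no more severe or serious events, because no such claim is planned.

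Finally, the SAP's Introduction allows extra analyses after database lock, identified in the publication. A later breakdown is therefore not barred, but it would not be pre-specified.

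**Conclusion.** The point holds as a gap in planned reporting. After 24 hours the SAP gives AE counts by arm but no type or grade, and it gives no SAE result by arm at any time. This affects one of three post-treatment AE interviews in all three countries, because the tables are produced per country. The share of events affected is not given in the documents and cannot be derived from them.

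Two assumptions are made. The *After 24h* column is taken to hold the 3-week interview, since no other AE capture is scheduled after 24 hours. The two tables are taken to be the whole planned safety output, as the SAP's wording indicates.

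The primary efficacy result is untouched. The change should still be made, because safety is a stated objective, the information is collected, and safety output is best fixed before results are known.

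**What to change.** First reconcile the Pemba protocol's SAE reporting window (section 6.1.4) with its own schedule of visits (section 4.6) and the SAP's Time and Events Table, so that the SAE summary has one stated window for each country.

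Then, in the SAP's Safety analysis:

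- Add a block for the period after 24 hours to day 21 to the specific-event table, with ALB, IVM-ALB and total, each with any grade and grade above 2. The table grows from 18 to 4 × 3 × 2 = 24 columns.
- Retitle the first table so that it names the period after 24 hours, which it already contains.
- Add a row for participants with at least one SAE, by arm and country, and a listing of each SAE giving type, day, grade and relatedness.

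The cost is revised table shells and minor programming on data already collected. No visit is added and no efficacy analysis changes.
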